
Confidentiality, privacy, protection of data:

Risks will be minimized by not including personal identifying information on the forms, when possible, and by conducting interviews, functional assessments, and collection of personal information in a secure telehealth platform. All data will be collected using unique patient identification codes. All evaluation forms, reports, and other records will be identified by a coded number to maintain participant confidentiality. All records will be stored in a locked file cabinet. Study data will be collected and managed using REDCap (Research Electronic Data Capture). Clinical information will not be released without written permission of the participant, except as necessary for monitoring by the IRB or NIH. Finally, subjects will be monitored for evidence of distress associated with study completion. Any subjects who express a desire for additional support will be referred to mental health services by [name] via established clinical referral pathways.

E. Potential Scientific Problems:

Potential Recruitment Difficulties: Due to uncertainty surrounding the COVID-19 pandemic, there may be difficulty recruiting 45 participants for the study. For September 22-23, 2020, the current census of COVID-19 positive patients in UHealth hospital was 23 of which 2 were new admits in the past 24 hours. In the same time period, there were a total of 27 admitted patients (1 new in past 24 hours) who tested positive for COVID-19 in hospitals affiliated with the University of Colorado.

Missing Data: All participants with outcome measurements will be included in analysis. The importance of reassessment for data collection will be stressed during enrollment and consent and repeated during study participation. Participants will be contacted repeatedly if they miss reassessment time points, and all efforts will be made to collect data.

Technical Issues: Technical issues are a concern for telerehabilitation and telehealth programs. As such, we have a detailed approach to address any technical issues which may arise.

1. Participants may call the Research PT (or designee) anytime, during regular business hours, with issues or concerns.
2. If a technical issue should arise that the Research PT cannot address, they will contact Blue Marble's Research Associate, [name], to discuss.
3. If needed, [name] will speak directly with the participant to solve the issue.
4. Although unlikely, Blue Marble's programmer may need to participate on the call to resolve the issue. The programmer has human subjects training.
5. The Research PT (or designee) will keep track of any and all technical issues as this is a feasibility outcome of the study.

F. Data Analysis Plan:

Sample Size: We estimate the proportion of participants at any session with technical difficulties (anticipate $\leq 20\%$), use the platform between sessions (anticipate $\geq 50\%$), and adhere to the intervention (anticipate $\geq 50\%$). Assuming these rates, a sample size of 30 and a two-sided 95% CI, provides a margin of error of 15% for technical difficulties and 18%, for platform use and adherence. We use preliminary 5-time chair rise data to estimate our effect size ($SD=8.7$) in our outcome and assume adjustment variables, including baseline measures, will explain at least 50% of the total variance (R^2). Using linear regression, we anticipate the width of our 95% confidence interval for the group coefficient to be $\pm 0.90 \times 1$ SD at week 6. We anticipate additional precision by using all longitudinal outcome data. We will also provide descriptive statistics for the change from baseline over time, for each group.

We hypothesize (B) tele-rehabilitation is associated with improved physical function in participants previously admitted to the hospital, as measured by change in the 30" Chair Stand Test at 12 weeks. Randomization will be stratified by age (<55 , ≥ 55), sex, and length of mechanical ventilation (< 5 days, ≥ 5 days). Hypothesis A: Descriptive statistics will assess feasibility (i.e., adherence, SUS score, and safety). Hypothesis B will be analyzed with group assignment (AFTER program versus control) as the primary explanatory variable; secondary analyses will be made to COMIRB 20-0703 cohort. Analyses will utilize R (<https://www.R-project.org>), SAS (Cary, NC), and GraphPad Prism (San Diego, CA). Code will be portable and reproducible with documenting libraries and raw data location, as well as code documenting cleaning.

G. Summarize Knowledge to be Gained:

The proposed study will 1) address a great and urgent need to identify predictors of multisystem recovery and long-term health in survivors of COVID-19 and 2) evaluate rehabilitative care to these individuals even, and especially, when they face post-hospitalization barriers to in-person care.

H. References:

References

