Our overarching hypothesis is that both healthy middle-aged and older adults with multimorbidity who experience the 'accelerated aging' effects of profound inflammation associated with COVID-19 will experience significant ongoing physical and neuropsychological impairment (Aim 1 of parent grant, approved through COMIRB 20-0703 and COMIRB 20-0690). Novel, scalable interventions that can overcome many of the barriers imposed by COVID-19 are urgently needed to reverse physical and neuropsychological impairments and prevent the long-term functional consequences (Aim 2 of parent grant, described in this protocol). We will investigate this hypothesis through the following aim:

Aim: Investigate the feasibility and initial efficacy of a multicomponent tele-rehabilitation program during COVID-19 recovery.

Hypothesis A: Tele-rehabilitation is safe and feasible. We anticipate that no injuries will occur, ≤20% of telehealth sessions will experience technical difficulties, ≥50% of participants will adhere to the exercise program, and ≥50% of participants will use the Platform between face-to-face online sessions.

Hypothesis B: Participation in tele-rehabilitation improves physical function (measured by 30 Second Chair Stand Test) compared with controls.

This study will contribute immediately to our knowledge of the course of recovery for survivors of COVID-19 and will advance the feasibility of tele-rehabilitation as a more generally useful intervention in patients lacking access (distance, availability, mobility) to standard rehabilitative services. Overall, development of effective tele-rehabilitation programs as alternatives to delivering rehabilitation to populations lacking access could transform the way in which we deliver acute rehabilitation and post-hospital care for all patients.

II. Background and Significance:

Significance of the proposed research centers on: 1) the recent COVID-19 pandemic that has unknown impacts on long-term health among patients who survive the disease; and 2) the need to deliver care to patients who are recovering from COVID-19 while concurrently in quarantine or with limited in-person care availability.

COVID-19 is a Pandemic with Unknown Long-Term Impacts on Health

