Outcomes, unless specified otherwise, will be collected at baseline, week 6 (primary endpoint), week 12, and week 26. Baseline testing will occur following the pre-session to set up the Platform and prior to the Physical Therapy Evaluation (session 1). The primary functional outcome for Hypothesis B (30" chair stand test) will be collected through the Platform (more details below). Each test session will include the standardized procedures described in the next sections. Importantly, all test sessions will occur in the participant's home and when possible, be facilitated via the Platform and verified concurrently by a trained outcomes assessor who oversees the testing remotely.

Feasibility (Hypothesis A) will be measured by program adherence, defined as the number of sessions attended divided by the total number of prescribed sessions (n=12). Individuals will be considered adherent if they attend at least 75% (9 visits) of the total sessions. Secondary adherence will be measured by the number of days the HEP is completed divided by the total number of prescribed sessions (n=60 [5x/12 weeks]), with adherence defined by completion of ≥ 75% (45 sessions) of prescribed sessions. System Usability Scale (SUS) will be collected at program end only. The SUS is a 10-item survey that uses a 5-point Likert scale (Strongly disagree (1) to Strongly agree (5)). Scores range from 0 to 100 and higher scores indicate better usability. It is a valid scale and is frequently used by the Platform to assess its usability. Safety will also be measured as a marker of feasibility. Safety events will be categorized and counted; safety events will be collected during each session and through the diary feature on the Platform. Additionally, falls will be graded using the Falls-Grading Scale.⁸³ The scale ranges from 1 to 4; a grade of 1 is defined as a near fall, grade 2 is a fall that does not receive medical attention, grade 3 is a fall that requires medical attention but no hospital admission, and grade 4 is a fall resulting in hospital admission. All the aforementioned outcomes will be collected in the intervention group, and only safety will be collected in the control group.

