In addition to the data regarding comorbidities and hospitalization which is collected through medical record review as part of COMIRB 20-0690 and 20-0703, data will be collected through the Platform. The Platform can track usage data, results from tests and measures, and health information. Usage data will be used to monitor and describe adherence to prescribed activities (e.g., Home exercise program, learning modules). It will also be used to collect the following outcomes: 30" Chair Stand Test, Timed Up-and-Go test, 4-stage balance test, system usability scale, activities-specific balance confidence (ABC) scale, and the PROMIS Scale v1.2 Global Health. While participants will be encouraged to use the Platform for this data collection since it is part of our feasibility outcome, alternatives will be provided for the main testing points (baseline, week 6, week 12 and week 26) to achieve complete data collection. Through the health diary feature, participants will be encouraged to log data pertaining to but not limited to medical history (medications, comorbidities), smoking status, demographics (age, gender, height, weight), and health events (e.g., hospitalization, injury, fall). This data entry is optional and completed via self-report. Any data entered into the Platform will be accessible by the research team. The participant's name is NEVER associated with the Platform in any way, and once a participant is enrolled, he/she will be assigned a login/password such as "Telerehab_P01" to indicate telerehabilitation study and participant 01; the initial account password is randomly generated through Blue Marble's webapp.

B. Description of Population to be Enrolled:

Potential participants will be recruited ideally during the first 2 to 6 weeks following hospital discharge to home, though if recruitment targets are slow, enrollment will be allowed up to 12 weeks post-discharge to home.

Inclusion Criteria:

1. Confirmed COVID-19, per diagnostic criteria (PCR testing)
2. Hospitalized for at least 24 hours
3. 35 years of age or older
4. Able to provide informed consent
5. Internet capability to access the platform
6. Community-dwelling prior to hospitalization

Exclusion Criteria:

1. Unstable medical comorbidities that would preclude participation in exercise
2. Receipt of >1 session of outpatient physical therapy

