Participants will begin the AFTER program following enrollment into the study and randomization to the intervention group. The program was developed around key elements of rehabilitation that patients and providers have identified as important aspects: 1) ability to communicate with healthcare providers, 2) ability to monitor response to exercise and progress, and 3) individualized care that changes based on a person’s response.⁸¹ The rehabilitation program follows current recommended guidelines and includes therapeutic exercises, functional activities, balance training, and aerobic conditioning.²⁶

The program will consist of 12 individual sessions. There will be 3 sessions during the first week, 2 sessions per week during weeks 2-4, 1 session per week during weeks 5-6, and 1 booster session during week 9 or 10. Therapists will be instructed on the standardized protocols for individual sessions. During weeks 7-12, in addition to the booster session, if adherence to the HEP drops below 75% as measured through the Platform, the therapist will follow up with the participant.

Platform.

The Platform is a combination downloadable app (patient-side) and web-app (administrative-side) software tool that contains digital translations of standardized, evidence-based tests, exercises, and educational modules for a variety of conditions (Figures 1&2). The Platform will be used to facilitate multicomponent tele-rehabilitation. Participants will use the app to test and track their physical function, perform avatar-guided exercises, and obtain educational content. The ability to track their activity

Figure 1. How the Platform works.

minutes, repetitions, changes in resistance difficulty, and session participation will provide necessary feedback for the biobehavioral strategies. The educational content is based on current clinical practice guidelines and recommendations from the National Institute of Health (NIH). Core educational modules will be assigned on topics including the following: management of anxiety and depression, breathing techniques, and healthy eating.

[figure not shown]

Figure 2. Activities Dashboard.

Figure 3. Example of avatar-led exercise

Therapists can assign personalized avatar-led home exercise programs (Figure 3) to the participant allowing for individual-level modifications to the rehabilitation program. The participant logs into the app, and data is sent instantaneously to the supervising researcher to inform care plans.

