Promotion of Problem Solving	Collaborative generation of solutions to overcome barriers to goal attainment.	Participant generates solutions to identified barriers to goal attainment.
Action Planning	Collaborative activity goal generation. Therapist guides, using 5-10% increase from daily activity minutes from previous week target.	Participant-led weekly goal generation. Therapist ensures independence in action planning.
Encouragement	Therapist reviews plan for the next week, while encouraging participant on successes attained toward improved physical health.	Participant leads the review of the plan for upcoming week.

* Each week will have a specific “take-home” message linking physical activity and movement behavior to health. Messages will be brief and based on research evidence.

Home Exercise Program (HEP).

The HEP will include therapeutic exercises, functional activities, balance training, aerobic conditioning, and breathing practice. Specific exercises will be selected based on results from the physical therapy evaluation, and subsequent adjustments will be made based on patient preference and priorities which will be enhanced in the biobehavioral interventions. In preparation for weeks 7-12, participants will be educated on how and when to progress strengthening and aerobic exercises, and they will take a more active role in determining their own progression. Participants will collaborate with the therapist to develop a robust program. The therapist will remotely monitor as described above, and participants will be responsible for progressing their exercises.

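### The main time point for Hypothesis B is contradictory: week 6 is labelled primary and carries the precision figure, but the analysis plan states the hypothesis at 12 weeks

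*Combined protocol and SAP*

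**What the plan says.** Three statements bear on the main time point of Hypothesis B.

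- Section A (Outcome Measures, Data Collection and Outcomes): "Outcomes, unless specified otherwise, will be collected at baseline, week 6 (primary endpoint), week 12, and week 26". The same paragraph names the 30-second chair stand as the primary functional outcome for Hypothesis B.
- Section F (Data Analysis Plan), Sample Size: the 95% confidence interval for the treatment comparison is given as "group coefficient to be $\pm 0.90 \times 1$ SD at week 6".
- Section F, the following paragraph: Hypothesis B is stated as change in the "Chair Stand Test at 12 weeks".

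The other relevant places do not choose between the weeks. The Aims state Hypothesis B as "Participation in tele-rehabilitation improves physical function (measured by 30 Second Chair Stand Test) compared with controls", with no week. Later descriptions of the chair stand in sections A and C call it the primary outcome, also without a week. The part of section A on Platform data treats all visits alike: "alternatives will be provided for the main testing points (baseline, week 6, week 12 and week 26".

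On delivery, section C schedules three sessions in week 1, two per week in weeks 2 to 4, then "1 session per week during weeks 5-6, and 1 booster session during week 9 or 10". The home exercise text adds: "In preparation for weeks 7-12, participants will be educated on how and when to progress strengthening and aerobic exercises".

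**The concern.** The outcome and the group comparison are the same in all three statements; only the week differs. Someone writing the analysis from section A would take week 6 as primary. Someone writing it from the hypothesis sentence in section F would take week 12.

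Two things are at stake. First, the main efficacy contrast could be settled after both results are known, and each choice could cite protocol text. If the true effects at the two visits are similar, choosing the more favourable one overstates the effect. Second, if the true effects differ, the choice decides which question is answered: the effect at the end of the session-based phase, or the effect after a further six, mainly self-directed weeks.

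**Working it through.** **The texts side by side**

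| Place | Week | Status given |
|---|---|---|
| Aims, Hypothesis B | none | hypothesis |
| Section A, outcome schedule | 6 | labelled primary |
| Section A, Platform data | 6, 12 and 26 alike | main testing points, with baseline |
| Section F, precision of group coefficient | 6 | basis of the precision figure |
| Section F, statement of Hypothesis B | 12 | hypothesis |

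Week 6 has the stronger support, and week 12 is never called primary. But the only sentence that both names Hypothesis B and attaches a week to it says 12.

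**The two visits are different contrasts.** Cumulative sessions at the end of weeks 1 to 6 are 3, 5, 7, 9, 10 and 11. The booster in week 9 or 10 makes 12. So 11 of 12 sessions precede the end of week 6. After that there is one booster, plus therapist follow-up if home-exercise adherence falls below 75%.

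**The plan's own precision figure.** Inputs are 30 intervention and 15 control participants (the design-change paragraph before Research Design and Methods) and R² = 0.50 (section F).

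- SE in SD units = √(1 − 0.50) × √(1/30 + 1/15) = 0.7071 × 0.3162 = 0.224.
- With t on 42 df (2.018), the half-width is 0.451 SD and the full width 0.902 SD.

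The figure 0.90 therefore reproduces as a full width, not as the printed ± half-width. That is a separate defect. The calculations below use the SE of 0.224 SD that follows from the stated inputs. If ±0.90 were taken literally, the SE would be 0.90/2.018 = 0.446 SD and every SD-unit result below would roughly double. Results in SE units would not change.

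**Effect of reporting the more favourable visit.** Assume normal errors, equal precision at both visits, and correlation ρ between the two estimates. The documents do not give ρ, so 0.5 to 0.9 is shown. If the true effects differ by d standard errors, the selected estimate exceeds its own visit's true effect on average by θ·φ(d/θ), where θ = √(2(1 − ρ)) and φ is the standard normal density. For d = 0 this is √((1 − ρ)/π).

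| ρ | d = 0: SE (SD) | d = 0.5: SE (SD) | d = 1: SE (SD) |
|---|---|---|---|
| 0.5 | 0.40 (0.089) | 0.35 (0.079) | 0.24 (0.054) |
| 0.7 | 0.31 (0.069) | 0.25 (0.056) | 0.13 (0.030) |
| 0.8 | 0.25 (0.056) | 0.18 (0.041) | 0.07 (0.016) |
| 0.9 | 0.18 (0.040) | 0.10 (0.021) | 0.01 (0.003) |

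Here d = 0.5 and d = 1 are differences of 0.11 and 0.22 SD between the true effects.

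**Where the 95% intervals miss, equal true effects (d = 0)**

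| ρ | Wholly above truth | Wholly below truth | Total |
|---|---|---|---|
| 0.5 | 4.5% | 0.5% | 5.0% |
| 0.7 | 4.2% | 0.8% | 5.0% |
| 0.8 | 3.9% | 1.1% | 5.0% |
| 0.9 | 3.5% | 1.5% | 5.0% |

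Without selection, 2.5% would fall on each side. Total coverage is unchanged, but the errors become lopsided. A simulation of 4 million draws per correlation agreed with these formulas.

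**The case against.** The best defence is that week 6 is plainly primary. It is the only visit so labelled, and the precision sentence concerns the group coefficient, which belongs to Hypothesis B alone. On this reading the 12-week phrase is loose drafting about the end of the intervention, and presenting week 12 as primary would contradict a public label. The point about textual weight stands: the ambiguity is not symmetric. It does not remove the conflict, because the 12-week wording sits in the analysis plan, where an analyst would look for the hypothesis.

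A second reading treats week 12 as the exception allowed by the qualifier in the section A schedule. That qualifier governs when outcomes are collected, not which visit is primary. Section F also gives the precision of this very comparison at week 6.

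Third, the trial is a 45-person pilot with no test, alpha or power for Hypothesis B. Section F expects extra precision from all the longitudinal data and adds: "We will also provide descriptive statistics for the change from baseline over time, for each group". This stands in part. It limits the harm and makes a selected visit easier to notice, but it does not say which between-group contrast is the main one.

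Fourth, a registered primary time point might limit the choice. The registry record was not available for this review, and a registry entry would not make the protocol text consistent.

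References to a 6-week programme and a 12-week intervention are not a further contradiction, because section C describes one programme in two phases.

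**Conclusion.** The concern holds. The protocol labels week 6 primary and gives its precision there, yet states the hypothesis at 12 weeks, and no section we have reconciles the two. This should be fixed, although it does not undermine the trial.

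The numerical consequence is modest. At most it is 0.089 SD with equal true effects and ρ = 0.5, about one fifth of the 0.451 SD half-width, and it shrinks as the true effects diverge. These sizes rest on an assumed correlation, equal precision at both visits, the SE of 0.224 SD, and a rule of always reporting the better visit. The contradiction depends on none of them. The harm is selective reporting and uncertainty about which effect is being estimated; no planned test fails.

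**What to change.** Before any comparison of outcomes by group, name one primary time point for Hypothesis B and use it in both sections A and F.

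- **Simplest:** change the Hypothesis B sentence in section F to week 6, which matches the label and the precision statement. Report weeks 12 and 26 as secondary contrasts from the longitudinal analysis.
- **If week 12 is intended:** change the label in section A and restate the precision for week 12. The week 6 figure carries over only if retention and R² are the same. As assumed illustrations (t with the number analysed minus 6 df), 10%, 20% or 30% missing gives half-widths of 0.48, 0.51 or 0.55 SD. R² of 0.40 or 0.30 with nobody missing gives 0.50 or 0.54 SD.

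The cost is a minor amendment to an IRB-approved protocol. No new data are needed, because the chair stand is already scheduled at weeks 6, 12 and 26 in both groups.
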